- Listening effort and fatigue (Effort Assessment Scale, EAS; Fatigue Assessment Scale; FAS; Listening Effort Questionnaire-Cochlear Implant, **LEQ-CI***) at 1, 3, 6, and 9 months post first treatment activation
- Tinnitus severity (Tinnitus Functional Index, TFI) at 1, 3, 6, and 9 months post first treatment activation
- Tinnitus loudness (Visual Analogue Scale of Loudness, VAS-L) immediately before and after first treatment activation and at 1, 3, 6, and 9 months post first treatment activation
- Mood (Hospital Anxiety and Depression Scale, HADS) at 1, 3, 6, and 9 months post first treatment activation
- Hearing-specific quality of life (Nijmegen Cochlear Implant Questionnaire, NCIQ; York Binaural Hearing-Related Quality of Life, YBHRQL; Hearing Handicap Inventory for Adults, HHIA) at 1, 3, 6, and 9 months post first treatment activation
- Health-related Quality of Life (EuroQol EQ-5D-5L; Health Utilities Index Mark 3, HUI3; ICEpop CAPability measure for Adults, ICECAP-A) at 1, 3, 6, and 9 months post first treatment activation
- Global ratings of change in hearing and quality of life at 1, 3, 6, and 9 months post first treatment activation: At each follow up appointment following first treatment activation, participants will be asked to indicate on 7-point Likert scale ranging from 'Much Worse' to 'Much Improved' whether hearing and quality of life have improved or worsened relative to two anchor points: (1) immediately prior to first treatment activation; and (2) since the last trial appointment.
- Device usage (participant self-report) at 1, 2, 3, 4, 5, 6, 7, 8 and 9 months

*Data to be collected using LEQ-CI questionnaire once licence is in place

Safety outcomes

From randomisation to 9 months post first treatment activation, safety data, including number of expected AEs and SAEs and unexpected related SAEs will be summarised with descriptive statistics according to the treatment the participant received, irrespective of randomisation. Where a participant did not receive their allocated treatment but had an expected AE, or SAE this will be indicated.

Stopping rules and discontinuation

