The TSC will meet at least once a year or as required and will provide independent oversight of the trial on behalf of the trial sponsor.

The DMC will meet at least once a year or as required to assess safety, effectiveness and futility of the trial and will report to the TSC.

The Trial Management Group (TMG) will meet more frequently, at least every two months, and will be responsible for the day-to-day management of the trial.

The Chief Investigator has overall responsibility for the trial and shall oversee all trial management.

The data custodian will be the Chief Investigator.

DURATION OF THE TRIAL AND PARTICIPANT INVOLVEMENT

Trial Duration: The trial will continue recruiting until study end date. Participant follow-up will continue for approximately 18 months following the end of recruitment. Recruitment progress and timelines will be monitored against projected recruitment and overall trial timelines will be adjusted, as necessary.

Participant Duration: Individuals will participate in the trial for up to 18 months from initial consent to final follow-up: The COACH eligibility pathway could take up to 6 months, with a further 3 months from baseline and randomisation to treatment(T0), and primary outcome collection at 9 months post T0.

End of the Trial

The end of the trial will be the final database lock.

SELECTION AND WITHDRAWAL OF PARTICIPANTS

Recruitment

Potentially eligible participants will be identified through patient database searches of audiology clinics at sites and Participant Identification Centres (PICs) for patients who do not have a cochlear implant and who may meet the inclusion criteria for the trial based on their most recent audiometric assessment. Potential participants may also be identified through a

database search at a GP practice working as a PIC. The initial approach will be from the patient's usual care team or cochlear implant service which has previously assessed them for CI suitability and may involve NIHR Clinical Research Network staff to whom recruitment activities have been delegated by the local PI; this may be in person, via text or via a letter, patient information leaflet and expression of interest (EOI) form sent to the potential participant from the audiology department or GP practice where they are registered. Where an information pack is sent in the post, the full-length participant information sheet (PIS) and defined pre-screening questions may also be included, dependent on site preference.

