The AB Word test in quiet at 70 dBA will only be administered at the consent visit and will not be repeated at the baseline visit. This choice is to ensure that the use of the AB Word test to assess eligibility aligns with its use in routine clinical care, where meeting the AB word test criterion defined within NICE guidelines at one timepoint is sufficient to proceed to cochlear implantation, if all other criteria are met.

At this point in the eligibility pathway, trial sites may use their own speech testing equipment, or equipment supplied by the COACH co-ordinating centre for use to administer the trial

eligibility and outcome assessments. If the trial sites use their own equipment for eligibility assessments, those assessments must meet the requirements of the trial assessments, including calibration records for the equipment, details of the test materials presented and the responses of the patient. The test must be completed either on the date of the consent visit or within the previous 3 months.

Throughout the trial, should there be a need to minimise face-to-face visits (e.g., due to a pandemic), any aspects of the COACH eligibility pathway that are both clinically appropriate and feasible to take place remotely can be introduced by sites, using any appropriate remote consultation IT systems that are provided by their Trust for use in routine practice.

If on the basis of above initial suitability checks the potential participant is still deemed potentially eligible, the COACH eligibility pathway will proceed according to current local standard procedures for CI suitability at each trial site. The CI suitability process is a multi-disciplinary process which includes a variety of wellbeing and physiological checks, including imaging, and a variety of health care professionals including audiologists, speech and language therapists and ENT surgeons. The COACH eligibility pathway will conclude with a decision of suitability for cochlear implantation made by an MDT.

Participant eligibility, as confirmed by agreement from the MDT, will need final sign off by a CI surgeon delegated the responsibility on the trial delegation log. Participants confirmed eligible will be invited to a baseline visit. All participants must be assessed and confirmed as eligible to receive a CI prior to randomisation to either arm.

Baseline Visit

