Comparator Arm	MRI (no ionising radiation) or Xray (~0.1 mSv) or CT Scan (~1 mSv)	N/A
Intervention Arm	MRI (no ionising radiation) or Xray (~0.1 mSv) or CT Scan (~1 mSv)	Xray (~0.1 mSv) or CT Scan (~1 mSv) or Cone Beam CT Scan (~0.05 mSv)

Although subjects in this trial are exposed to ionising radiation, the amount is low. A head X-ray delivers approximately a 1 mSv dose of ionising radiation. In comparison, the UK average radiation exposure for an individual is about 2.7 mSv (= 2,700 µSv; data obtained from Public Health England [PHE] Ionising Radiation Exposure of the UK Population: 2010 Review) per year. This radiation comes from natural sources, e.g., cosmic radiation, radon gas, and from average medical exposure. How much background radiation individuals are exposed to depends on many factors including geographical location, occupation and home ventilation. It is believed that any amount of radiation that is received carries a risk of later developing serious and possibly fatal conditions.

Ionising radiation has the potential to damage DNA, and cause mutations which have the potential to lead to diseases such as cancer. The risk associated with the maximum possible dose of radiation in this trial is very small and is considered to be acceptable.

Clinical Assessment

The ionising radiation exposures in this trial are all associated with the implantation of a cochlear implant and are additional to standard of care due to the fact that the cochlear implant itself is additional to standard of care for these participants. The exposures are required for the safe implantation of the device and, therefore, are clinically justified. Furthermore, the maximum dose associated with the surgical procedure is approximately 2 mSv [a planning CT and a post-surgical CT] which is less than the average UK annual background radiation dose. The additional risk associated with this maximum dose is approximately 1 in 12,000 of inducing harm from cancer induction which equates to an approximate 0.02% increase in the natural risk of harm from cancer.

Covid-19

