The number of participants experiencing at least one AE or SAE will be summarised using descriptive statistics. The total number and type of AEs and SAEs will also be summarised, overall and by event.

Procedures for missing, unused and spurious data

It is planned that several strategies to investigate the effect of missing primary outcome data will be undertaken as sensitivity analyses, including the use of multiple imputation with chained equations and minimisation variables as covariates. More information on methods will be included within the SAP.

Definition of populations analysed

Full analysis set, including safety: All randomised participants for whom at least one post-baseline assessment is available.

There will not be a per-protocol dataset.

ADVERSE EVENTS

Reporting requirements

The collection and reporting of Adverse Events (AEs) will be in accordance with the UK Policy Framework for Health and Social Care Research 2017 and the requirements of the Research Ethics Committee (REC). Definitions of different types of AEs are listed in the table of abbreviations and definitions.

Reporting Period

Trial related AEs will be collected from time of randomisation (baseline visit) until the collection of the primary outcome (9 months post-treatment onset).

Definitions

Adverse Events

An **adverse event** is any unfavourable and unintended sign, symptom, syndrome or illness that develops or worsens during the period of observation in the trial.

An AE does include a / an:

1. exacerbation of a pre-existing illness.
2. increase in frequency or intensity of a pre-existing episodic event or condition.
3. condition detected or diagnosed after medicinal product/device administration even though it may have been present prior to the start of the trial.
4. continuous persistent disease or symptoms present at baseline that worsen following the start of the trial.

An AE does not include a / an:

1. medical or surgical procedure (e.g., surgery, endoscopy, tooth extraction, transfusion); but the condition that led to the procedure is an AE.
2. pre-existing disease or conditions present or detected at the start of the trial that did not worsen.
3. situations where an untoward medical occurrence has not occurred (e.g., hospitalisations for cosmetic elective surgery, social and / or convenience admissions).

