4. disease or disorder being studied, or sign or symptom associated with the disease or disorder unless more severe than expected for the participant's condition.
5. overdose of concurrent medication without any signs or symptoms.
6. expected AE as listed below.

Expected adverse events

The treatments provided to both intervention arms are widely available within the NHS, used in standard care and considered to be safe. Known adverse events (listed in the table below) are related to their respective trial interventions. These events are secondary outcomes and will be collected as part of the eCRF. The number of occurrences of expected AEs and SAEs will be regularly reviewed throughout the trial by the TMG and the DMC.

Expected AE	Expected SAE
Related to Cochlear Implantation (intervention arm only)	
Facial nerve stimulation (temporary)	Facial nerve stimulation (chronic)
Patient reported decreased hearing ability or loss of residual acoustic hearing (temporary or permanent)	The inability to use the implant or a hearing aid in that ear
Vestibular dysfunction (temporary)	Vestibular dysfunction (chronic)
Perception of non-auditory sensations (temporary or permanent)	Infection requiring hospitalisation (e.g., meningitis and the need for vaccination)
New onset or exacerbation of pre-existing tinnitus	Any surgical complication that requires hospitalisation
Altered taste	Need for revision surgery, reimplantation or explantation
Facial weakness	Subdural injury
Acute otitis media or any other infection treated by oral antibiotics	Chronic pain in or around the implant site or hearing aid
Perilymph fistula	

Expected AE	Expected SAE
Concurrent cerebrospinal fluid (CSF) leakage	
Subcutaneous haematoma	
Unsatisfactory device insertion (e.g., misplacement of electrode array, incomplete electrode insertion, tip fold-over)	
Failure of component parts	
Related to Hearing Aids (intervention and comparator arms)	
Ear infection	None
Exacerbation of eczema	

Serious Adverse Events

A Serious Adverse Event (SAE) is any adverse event occurring following trial mandated procedures that results in any of the following outcomes:

1. Death
2. A life-threatening adverse event
3. Inpatient hospitalisation or prolongation of existing hospitalisation
4. A disability / incapacity
5. A congenital anomaly in the offspring of a participant

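### Safety collection opens at randomisation, but trial-driven eligibility procedures can start up to 6 months earlier, so a serious event caused by the work-up falls outside the stated collection

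*Protocol*

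**What the plan says.** **Collection window.** Under Adverse Events, Reporting Period: "Trial related AEs will be collected from time of randomisation (baseline visit) until the collection of the primary outcome (9 months post-treatment onset"). The Safety outcomes paragraph of the Trial Design section gives the same start: "From randomisation to 9 months post first treatment activation, safety data, including number of expected AEs and SAEs and unexpected related SAEs will be summarised". Appendix 1 first schedules an adverse-effects check at treatment activation, with none at consent or baseline.

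**Procedures before the window.** The COACH Eligibility Pathway section starts assessment once consent is received. Those who pass the initial hearing, speech, history and hearing-aid checks go on to a work-up that "includes a variety of wellbeing and physiological checks, including imaging". The section on trial duration and participant involvement gives the timing: "The COACH eligibility pathway could take up to 6 months, with a further 3 months from baseline and randomisation to treatment(T0").

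**Status of the imaging.** The Clinical Assessment paragraph of the ionising radiation section says that the trial's radiation exposures "are additional to standard of care due to the fact that the cochlear implant itself is additional to standard of care". The table in that section lists eligibility-pathway imaging for both arms.

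**SAE definition.** An SAE is "any adverse event occurring following trial mandated procedures that results in any of the following outcomes". It names neither randomisation nor a device.

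**The concern.** The protocol makes people undergo procedures because of the trial and defines a serious event by reference to such procedures. It then opens safety collection only after those procedures are finished. Anyone working from the Reporting Period section would have no instruction to report a serious event arising during the work-up.

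The gap matters most for people who consent, go through some or all of the work-up and are then found ineligible. They never reach randomisation, so their events cannot enter the trial's safety data. At stake is whether the trials unit, the sponsor and the DMC would see serious harm from procedures that the trial itself imposes.

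**Working it through.** **1. Length of the uncovered period.** Inputs are from the section on trial duration and participant involvement: eligibility pathway up to 6 months, 3 months from baseline and randomisation to treatment, 9 months of follow-up.

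- Plan's own total: 6 + 3 + 9 = 18 months. This reproduces the stated maximum: "Individuals will participate in the trial for up to 18 months from initial consent to final follow-up".
- Covered by the safety window: 3 + 9 = 12 months.
- Uncovered: 18 − 12 = 6 months, and 6/18 = 33% of maximum participation.
- Lower end: the Informed Consent section requires at least two weeks between the initial eligibility visit and randomisation, so the gap is not normally zero.

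These are calendar spans. The procedures within them are discrete visits, so 33% is not a share of risk.

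**2. Does any other provision close the gap?** Suppose a serious event is caused by the work-up before randomisation.

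| Step | What the protocol provides | Result for this event |
|---|---|---|
| Is it an AE? | Must arise within the trial's period of observation, which is not defined (Definitions, Adverse Events) | Unclear; a site may read it as the Reporting Period |
| Is it an SAE? | Must follow a trial mandated procedure (Serious Adverse Events) | Yes, if it counts as an AE |
| Can it be rated related? | Every causality category refers to the trial device (Causality); related SAEs are those tied to trial treatment or intervention (SAE procedure at NCTU; SAEs) | No category fits, as no trial device has yet been supplied |
| Does it reach the eCRF? | Only related or suspected related SAEs, apart from the listed expected events (Recording and Reporting) | Not reliably |
| Is it in the safety summary? | The analysis set, which includes safety, is limited to randomised participants (Definition of populations analysed) | Never, if the person was not randomised |
| Other routes | Medical record; SAE form within 24 hours of awareness, with no start date given; ethics committee told of a significant safety issue | Possible, but the second depends on the unclear steps above and the third on an issue already having been recognised |

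**3. Size of the one hazard the protocol quantifies.** The ionising radiation section gives a maximum of about 2 mSv with a risk of about 1 in 12,000, and about 1 mSv for an eligibility CT. Assuming that risk is proportional to dose, one eligibility CT carries about 1 in 24,000 (12,000 × 2). If all 130 randomised participants had one, the expected number of cases is 130/24,000 = 0.005. The number consented is not stated, so the figure for all consented people cannot be given.

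**4. Effect on the comparison.** The uncollected events precede allocation. They cannot differ by treatment received, and the sample size does not depend on them.

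**The case against.** The strongest defence is that the text can be read consistently. The two statements of the window agree with each other. The SAE definition says what an SAE is and sets no collection period. If the observation period means the Reporting Period, events before randomisation are simply not trial AEs. The safety objective concerns the safety of cochlear implantation and hearing aids, and a window from randomisation serves that. This stands to the extent that a reader who infers a flat contradiction goes too far: there is a mismatch that turns on an undefined term.

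A reader might also infer that serious harm from the work-up would never be captured. The protocol does not support that. All AEs and SAEs go into the medical record, sites must complete an SAE form on awareness with no start date stated, and significant safety issues go to the ethics committee.

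Nor does every consented person have the full work-up for the trial's sake. Only those still potentially eligible after the initial checks proceed to imaging. Under Recruitment, patients recently assessed for an NHS implant may reuse tests from the last 3 months. Most centres use MRI, and the additional-to-standard-care statement concerns ionising radiation only.

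Finally, moving the start date would not detect a late radiation-induced cancer. That is correct, but it does not dispose of the point: an acute serious event linked to a work-up visit is the kind of event that a collection rule exists for, and the protocol leaves its handling unclear.

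**Conclusion.** The point holds as a minor safety-reporting inconsistency. A serious event caused by the eligibility work-up is outside the stated trial safety collection for up to 6 of 18 months. For someone consented but not randomised, no clear path leads to the trials unit or the DMC beyond the medical record and the undated SAE-form and ethics-committee provisions.

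The conclusion assumes that at least some participants have the work-up because of the trial, which the ionising radiation section itself states for radiation exposures. It also assumes that sites follow the Reporting Period as written. The protocol does not give the proportion of participants who reuse NHS tests or the number consented, so the number of people affected cannot be stated. Events should be rare. A reader might infer that the comparison of safety between arms is biased; it is not, because the events precede randomisation. The efficacy analysis is untouched.

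**What to change.** - **Reporting Period:** collect and report SAEs possibly related to a trial mandated procedure from signed consent, in everyone consented, whether or not later randomised.
- **Definitions:** define the period of observation to match.
- **Causality, and the relatedness wording in the SAE reporting sections:** extend them from the trial device, treatment or intervention to include trial mandated procedures. Changing the Reporting Period alone would leave a work-up event with no category under which to count as related, and so off the eCRF.
- **Safety summaries:** keep randomisation as the start of the between-arm AE summaries and list pre-randomisation SAEs separately, including those in people not randomised.

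The cost is a short amendment touching several sections, site training and a few extra SAE forms. Trial identity numbers are already allocated after expression of interest (Case Report Forms section), so people who are not randomised can be reported on the existing form.
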